### **3.3.3 Handling Missing Data in Descriptive Analyses**

When summarizing categorical variables, subjects with missing data are generally not included in calculations of percentages unless otherwise specified. When needed, the category of "Missing" is created and the number of subjects with missing data is presented.

When summarizing continuous variables, subjects with missing data are not included in calculations. No imputations are made.

### **3.3.4 Handling Missing or Partially Missing Dates**

Missing or partially missing dates will not be imputed at data level. However, assumptions for missing or partially missing dates for important variables will be made to allow inclusion of appropriate data records in the analyses. In general, the assumptions about the missing or partially missing dates, when needed, are made conservative to avoid overestimation of treatment effect and underestimation of adverse effects.

[figure not shown]
If a medication date or time is missing or partially missing, so it cannot be determined whether it was taken prior or concomitantly, it will be considered both as a prior and a concomitant medication.

If the partial AE onset date information does not indicate whether the AE started prior to treatment or after treatment, the AE will be classified as after treatment.

---

[Redacted text block containing several lines of text and a bulleted list item, all obscured by black bars.]

## 4 STUDY SUBJECTS

### 4.1 DISPOSITION OF SUBJECTS

The number of subjects screened, assigned (if Cohort 1)/randomized (if Cohorts 2, 3, or 4), and treated will be presented. The reason for exclusion from one or more analysis sets will be summarized.

Disposition will be summarized for the Safety Population. The frequency and percentage of premature discontinuations from the study prior to Month 6 will be presented by cohort and overall. The primary reason for non-completion of the study will be summarized. The details of the ‘Adverse event’, ‘Protocol violation’, ‘Investigator decision’, ‘Sponsor decision’, ‘Subject request’, ‘Lost to follow-up’, ‘Subject non-compliance’ or ‘Other’ will be included in a listing.

### 4.2 TREATMENT MISALLOCATIONS

For subjects with errors in treatment allocation, the following is described under which cohorts they will be reported for safety analyses:

For example, if subjects were:

- Assigned a cohort (regardless of error) but not treated, then they will be excluded for all safety analyses.
- For Cohorts 2, 3, and 4: Treated but not randomized, then by definition they will be reported under the cohort they actually followed for all safety analyses.

### 4.3 PROTOCOL VIOLATIONS

All protocol violations will be assessed and identified as “major” or “significant” by the sponsor. The final list of major protocol violations will be provided by the sponsor, and the criteria for significant protocol violation will be determined prior to the database lock. The significant protocol

---

 The ETDRS lines in order, from largest to smallest, are 20/800, 20/640, 20/500, 20/400, 20/320, 20/250, 20/200, 20/160, 20/125, 20/100, 20/80, 20/63, 20/50, 20/40, 20/32, 20/25, 20/20, 20/16, 20/13, 20/10.

violations will be summarized for the Safety population, and the details will be presented in a listing by subject and cohort.

#### **4.4 INCLUSION AND EXCLUSION CRITERIA**

A detailed listing of inclusion/exclusion criteria not met will be provided by subject for the Safety Population.

### **5 DEMOGRAPHIC AND OTHER BASELINE CHARACTERISTICS**

Descriptive statistics will be provided to document baseline demographic information. This information may be used to informally assess similarity of the randomized groups at baseline, although no formal comparison will be conducted.

Descriptive statistics with respect to subject characteristics at baseline will be displayed for the Safety population. When several measurements are available before the first administration of study drug, the baseline value is the last available value prior to first dose, except for the baseline visual acuity score and baseline intraocular pressure which are the mean of the screening and Day 1 pre-injection values.

The variables to be summarized are:

- Gender, Ethnicity, Race, Iris color, Age, Current smoking status, Study Eye, Region
- Prior ocular history, both eyes (by MedDRA preferred term, including number and percentage of all Subjects with at least one prior ocular history)
- Medical history (excluding ocular history) (by body system and preferred term, with number and percentage for both; including number and percentage of all subjects with at least one prior medical history)
- Prior surgeries/procedures (by body system and preferred term, with number and percentage for both; including number and percentage of all Subjects with at least one prior surgery/procedure)
- Vital signs (Height, Weight, Pulse, Blood pressure, Respiratory Rate)
- ECOG performance status
- Visual acuity, both eyes
- Tonometry, both eyes
- ECG
- Ophthalmic exam, both eyes (Motility, Lids/Lacrimal/Lashes, Conjunctiva/Sclera, Cornea, Anterior chamber activity: cells, Iris, Pupils, Lens Status, Vitreous haze, Vitreous hemorrhage, Posterior vitreous detachment, Optic nerve, Macula, Retinal vessels, Peripheral retina)

- Imaging Assessments, study eye
  - Fluorescein Angiography:
    - CNV location (extrafoveal, juxtafoveal, subfoveal)
    - CNV type (predominantly classic, minimally classic, occult)
    - Area of choroidal neovascularization (CNV) (defined as classic CNV + occult CNV + RPE staining in mm^2)
    - Area of total lesion (mm^2)
  - Optical Coherence Tomography (OCT)
    - SHRM within the center 1mm (yes/no)
    - SHRM (μm)
    - RPE elevation
    - Central subfield thickness (μm)

## 6 PRIOR AND CONCOMITANT MEDICATION

All prior and concomitant medications will be summarized separately by WHO Drug code (Version 3, SEP 2017) on the Safety population. Medication usage will be summarized according to the 2nd level (main therapeutic level) and the 4th level (preferred term level) Anatomic Therapeutic Chemical (ATC) classification. Subjects will only be included once in the summaries within each ATC 2nd level or ATC 4th level category. The summaries will include the number and percentage of all subjects with at least one concomitant medication, respectively.

## 7 SAFETY EVALUATION

All safety analyses will be performed on the Safety population. Missing values of safety data will not be imputed and safety summaries will be based on the observed cases.

[figure not shown]

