#### 2.1.1 Safety Endpoints

Safety endpoints include:

- Adverse events (AEs)
- Vital signs (respiration, heart rate, systolic and diastolic blood pressure, etc.)
- ECG recordings
- Ophthalmic variables (visual acuity, IOP, ophthalmologic examination, stereoscopic fundus photography, fluorescein angiography, and spectral domain optical coherence tomography)
- Laboratory variables (blood: hematology, renal function, hepatic function, and electrolytes; urine: urinalysis)

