### **3.3.2 Visit Windows**

The scheduled visits will be used in the analyses over time.

Missing scheduled follow-up visits will be substituted by an unscheduled or early withdrawal visit occurring within each follow-up visit window, if there is only one unscheduled or early withdrawal visit occurring within the window. If there are multiple unscheduled or early withdrawal visits occurring within the window, the closest one within the visit window will be used. If no unscheduled or early withdrawal visit occurred within the window, the visit will be considered as missing. The details are tabulated in **Appendix 1**.

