### 7.2 ETDRS VISUAL ACUITY

ETDRS Visual acuity values and changes from baseline will be presented in a summary table by visit and cohort for the Safety Population.

The principal visual acuity outcome measure will be the mean change in visual acuity (MCVA) from Baseline to Month 6. Supportive measures will be the percentage of subjects gaining  $\geq 5$ ,

$\geq 10$ ,  $\geq 15$ ,  $\geq 20$  letters, and losing  $\geq 0$ ,  $\geq 10$ , and  $\geq 15$  letters from Baseline to Month 6. Additionally, the number and percentage of subjects meeting each of the following criteria at Month 6 will be summarized: ETDRS Snellen Equivalent of 20/25 or better, ETDRS Snellen Equivalent of 20/40 or better, and ETDRS Snellen Equivalent of 20/125 or worse.

[Redacted text block]

[Redacted text block]

- [Redacted bullet point]
- [Redacted bullet point]
- [Redacted bullet point]

[Redacted text block]

[figure not shown]

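### The visible letter-loss percentages are defined only at Month 6 on observed cases, so a treated subject whose last visual acuity is earlier appears in none of them

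*SAP*

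**What the plan says.** SAP 2.1.1 lists visual acuity among the safety endpoints: "Ophthalmic variables (visual acuity, IOP, ophthalmologic examination, stereoscopic fundus photography". SAP 7.2 then gives two kinds of output in its visible text.

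- **By visit:** "ETDRS Visual acuity values and changes from baseline will be presented in a summary table by visit and cohort for the Safety Population". No loss percentage is attached to these visits.
- **At Month 6:** the categories of gain, then "letters, and losing $\geq 0$ , $\geq 10$ , and $\geq 15$ letters from Baseline to Month 6", and the Snellen categories, including 20/125 or worse.

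Four rules decide who enters the Month 6 percentages.

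- SAP 7: "Missing values of safety data will not be imputed and safety summaries will be based on the observed cases".
- SAP 3.3.2: "Missing scheduled follow-up visits will be substituted by an unscheduled or early withdrawal visit occurring within each follow-up visit window".
- SAP 3.3.2, for everyone else: "If no unscheduled or early withdrawal visit occurred within the window, the visit will be considered as missing".
- SAP 3.3.3: "subjects with missing data are generally not included in calculations of percentages unless otherwise specified". Where needed, a Missing category "is created and the number of subjects with missing data is presented".

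Other safety variables are handled differently. SAP 7.6 also reports vital signs as change to the last measurement, and SAP 7.7 also runs the eye-examination shift tables to the last available visit.

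**The concern.** Protocol 10.6 allows withdrawal for adverse events and treatment failure, among other reasons. It ends evaluation under the protocol for a subject who starts another treatment for neovascular AMD before completing study dosing. It also asks for the Early Withdrawal assessments on everyone who leaves, and the charts in Protocol section 3 include visual acuity at that visit. A withdrawn eye can therefore have a measured final acuity that no visible loss percentage uses.

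At stake is the completeness of a safety rate. With 10 or 20 subjects per cohort, one or two omitted eyes can separate a reported 0% from a rate that a reader would want to discuss. No test or power is affected, because the trial is descriptive.

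**Working it through.** **Rule trace.** Take a treated subject whose last acuity was measured before the Month 6 window.

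1. No visit falls in the window, so Month 6 is missing (SAP 3.3.2).
2. Nothing is imputed (SAP 7).
3. A subject with missing data leaves the percentage by default (SAP 3.3.3), and the visible part of SAP 7.2 does not specify otherwise.
4. The subject is therefore in neither numerator nor denominator of the letter-loss rates or of 20/125 or worse.

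**Inputs for the bounds.** The cohort sizes are 10, 10, 20 and 20 (SAP 2.3). They agree with the allocation: 50 subjects in a 1:2:2 ratio give 10, 20 and 20, and the 10 in Cohort 1 make 60. The plan gives no dropout rate and no expected loss rate, so there is no planned figure to reproduce. The values of m and x below are illustrations.

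**Formula.** Let n be the subjects in the cohort, m those with no Month 6 acuity, and x the losses seen at Month 6. The reported rate is x/(n − m). The rate in all n subjects lies between x/n (no missing eye would show the loss at Month 6) and (x + m)/n (every missing eye would). The width is m/n, which for one missing subject is 1/10 = 10 points or 1/20 = 5 points.

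| n | m | x | Reported | All-subject Month 6 rate |
|---|---|---|---|---|
| 10 | 1 | 0 | 0/9 = 0% | 0% to 10% |
| 10 | 1 | 1 | 1/9 = 11.1% | 10% to 20% |
| 10 | 2 | 0 | 0/8 = 0% | 0% to 20% |
| 20 | 1 | 0 | 0/19 = 0% | 0% to 5% |
| 20 | 1 | 1 | 1/19 = 5.3% | 5% to 10% |
| 20 | 2 | 0 | 0/18 = 0% | 0% to 10% |

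**What the bounds do not cover.** They concern status at Month 6. They say nothing about loss at any visit, which can be higher. For example, with n = 10, one subject missing, 0/9 at Month 6 and two completers who lost 15 letters earlier and recovered, the any-visit rate is at least 2/10 = 20%. The upper bound for Month 6 is 10%.

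**Scheduled post-baseline acuity tests** (charts in Protocol section 3), which matter for any-visit rates:

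- Cohort 1: 1 (Day 1 D2) + 10 (Months 1 to 5, D0 and D2) + 1 (Month 6) = 12, or 13 for subjects with the Day 9 visit.
- Cohort 2: 6 (Months 1 to 6).
- Cohort 3: 3 (D14) + 5 (Months 1 to 5) + 1 (Month 6) = 9.
- Cohort 4: 3 (D14) + 2 (Months 1 and 2, D0) + 6 (Months 3 to 5, D0 and D2) + 1 (Month 6) = 12.

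**The case against.** The strongest reply is that this is a claim of omission about a section that is partly blacked out. Redacted text follows directly after the visible loss categories in SAP 7.2. The visual acuity conventions in SAP 3.3.5 cannot be read, nor can Appendix 1, which sets the windows. A last-visit or any-visit table could be there, and who falls before the Month 6 window depends on Appendix 1. This stands. It limits the point to the visible text and makes the fix conditional.

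The second reply is that the data are largely reported already. Change from baseline is tabulated by visit with n, minimum and first quartile (SAP 3.3.1 and 7.2), all subject data are listed, discontinuations before Month 6 are given by cohort (SAP 4.1), and a vision loss may appear as an adverse event. This stands in part. A reader might infer that a withdrawn subject's loss vanishes from the report, and the documents do not support that. These routes are nevertheless incomplete:

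- A minimum shows whether some tabulated eye lost 15 letters at a visit, but not how many did.
- An early withdrawal visit replaces only a missing scheduled visit. As written, it is not used in the by-visit table when the scheduled visit in that window was attended.
- Protocol 12.1 excludes insufficient response from adverse events but allows an objective finding that leads to discontinuation, so the event tables may or may not show the loss.
- Listings hold the values but give no rate.

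A reader might also infer that the Month 6 rate understates harm. That does not follow. Protocol 10.6 also names cure and administrative reasons for withdrawal, and subjects who leave may have done better or worse than those who stay.

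**Conclusion.** The point holds on the visible text. A treated subject whose last acuity precedes the Month 6 window is in no visible vision-loss percentage, although the SAP also summarises vital signs and the eye examination at the last available measurement. Each such subject leaves 10 points (n = 10) or 5 points (n = 20) of the all-subject Month 6 loss rate undetermined. These widths are exact for Month 6 status and need no assumed dropout rate. How many subjects are affected, and which way the rate moves, cannot be known from the documents.

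This is a gap in safety reporting that should be closed. It is not evidence of bias, and it holds only if the redacted parts of SAP 7.2, SAP 3.3.5 and Appendix 1 do not already deal with it.

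A minor note: the printed loss threshold of at least 0 letters counts an unchanged eye as a loss. It may be an error in reading the PDF, or it may be meant as a no-gain category. The visible text does not settle which, so only a check against the source is warranted.

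**What to change.** Unless the redacted text already does so:

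1. Keep the Month 6 observed-case table.
2. For all Safety Population subjects with a post-baseline study-eye acuity, add the loss categories at the last available visit, including Early Withdrawal, labelled as not being Month 6 values.
3. Show the number missing Month 6 acuity in each cohort, using the Missing category that SAP 3.3.3 already allows.
4. As a separate measure, to which the bounds above do not apply, give the number and percentage in the same subjects with a loss of 15 letters or more at any post-baseline visit. Repeat it on the six monthly visits common to all cohorts (first visit of each month, Months 1 to 6) plus Early Withdrawal, because scheduled tests number 12, 6, 9 and 12 in Cohorts 1 to 4.
5. Check the threshold of at least 0 letters against the source and, if it is intended, label the row so that its meaning is clear.

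The cost is a few descriptive rows from data already collected, and one check. There are two drawbacks. Last values come from different times, and an any-visit rate picks up transient losses and rises with the number of tests, which the restricted version limits but does not remove.

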### 7.1 EXTENT OF EXPOSURE

Exposure to each study medication will be evaluated for each cohort and overall with respect to treatment duration (= Last injection date – First injection date + 31, in days), number of subjects treated at each planned visit, total injections received, using descriptive statistics (N, mean, standard deviation, median, minimum, Q1, Q3, maximum).

### 7.2 ETDRS VISUAL ACUITY

ETDRS Visual acuity values and changes from baseline will be presented in a summary table by visit and cohort for the Safety Population.

The principal visual acuity outcome measure will be the mean change in visual acuity (MCVA) from Baseline to Month 6. Supportive measures will be the percentage of subjects gaining  $\geq 5$ ,

$\geq 10$ ,  $\geq 15$ ,  $\geq 20$  letters, and losing  $\geq 0$ ,  $\geq 10$ , and  $\geq 15$  letters from Baseline to Month 6. Additionally, the number and percentage of subjects meeting each of the following criteria at Month 6 will be summarized: ETDRS Snellen Equivalent of 20/25 or better, ETDRS Snellen Equivalent of 20/40 or better, and ETDRS Snellen Equivalent of 20/125 or worse.

[Redacted text block]

[Redacted text block]

- [Redacted bullet point]
- [Redacted bullet point]
- [Redacted bullet point]

[Redacted text block]

[figure not shown]

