The current FDA approved pharmacologic therapies for NVAMD target and inhibit Vascular Endothelial Growth Factor (VEGF). VEGF is an endothelial cell survival factor and a mitogen. Endothelial cells are a key component of neovascular tissue. All approved anti-VEGF agents for NVAMD are administered by the intravitreal route of administration. These include Lucentis[®] (ranibizumab) and Eylea[®] (aflibercept) (Brown

et al., 2006; Heier et al., 2012; Rosenfeld et al., 2006).

In addition, although not labeled by the FDA for the treatment of NVAMD, the anti-VEGF agent Avastin[®] (bevacizumab) is currently used to treat ~50% of the eyes with NVAMD in the United States (Parikh, et al, 2017). A multicenter, prospective, randomized trial, funded by the US National Eye Institute, “The Comparison of Age-Related Macular Degeneration Treatments Trials” (CATT) demonstrated that monthly dosing with Avastin[®] 1.25 mg (0.05 mL) was non-inferior to monthly dosing of Lucentis[®] for eyes with NVAMD (Martin et al., 2012).

Avastin[®], Lucentis[®], and Eylea[®], on average, all improve the visual outcome in eyes with NVAMD. The primary functional impact of these anti-VEGF agents is to decrease intraretinal and subretinal fluid associated with abnormal blood vessels. Despite maximal therapy with intravitreal monotherapy anti-VEGF agents, the majority of patients do not achieve significant visual gain (≥ 15 letters of vision), and approximately 20% to 30% lose additional vision from baseline.

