4.6 Trial Rationale

There is widespread acceptance that the therapeutic benefit of anti-VEGF monotherapy is primarily a result of its potent anti-permeability effects. Studies have shown that VEGF is the most potent inducer of permeability in biologic systems (Dvorak et al., 1995). Multiple investigations of currently available anti-VEGF agents (Lucentis[®], Avastin[®] and Eylea[®]) suggest that they are essentially similar with respect to their safety and efficacy profiles (Brown et al., 2006; Martin et al., 2012; Rosenfeld et al., 2006; Schmidt-Erfurth et al., 2014). Furthermore, the “ceiling” of anti-VEGF mediated therapeutic benefit in NVAMD appears to have been reached as attempts at improving visual outcomes by altering the dose and regimen of anti-VEGF therapy have been unsuccessful (Busbee et al., 2013; Schmidt-Erfurth et al., 2014). Despite maximal therapy with intravitreal monotherapy anti-VEGF agents, the majority of patients do not achieve significant visual gain (≥ 15 ETDRS Letters) or achieve visual acuity of 20/40 or better. In addition, approximately 25% of the patients lose additional vision (Martin et al., 2012). Further, less than monthly regimen results in worse visual outcomes in the real world setting and over time patients in general lose vision with anti-VEGF monotherapy (Rakic et al. 2013, Rasmussen et al., 2013; Rofagha et al, 2013). Approximately one fifth of patients who had received anti-VEGF therapy developed GA within 2 years of treatment (Grunwald et al., 2014). The authors concluded that anti-VEGF therapy may play a role in the development of atrophy. At 5 years, the cumulative incidence was 38%, concluding that the development of GA was common after 5 years of anti-VEGF treatment (Grunwald et al., 2017).

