### 2.3 SAMPLE SIZE AND RANDOMIZATION

As this study is not designed to perform formal hypothesis testing, there is no formal sample size calculation. The sample size selected is based on a reasonable number of subjects to understand the safety variables of the proposed regimen and to improve upon the study design prior to performance of controlled trials that may be initiated in the future. Approximately 60 subjects will be enrolled, 10 subjects each in cohorts 1, 2 and 20 subjects each in cohorts 3, 4.

Once all subjects have been enrolled in cohort 1, subjects will be centrally allocated to one of the three remaining treatment cohorts using a randomization list generated by a block randomization.

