## 3.3 DATA HANDLING CONVENTIONS

### 3.3.1 General Conventions

Data will be analysed using SAS (Version 9.4 or later) or R. Descriptive analyses will be performed on baseline, safety data. All tables will be created with the 4 dosing cohorts presented in columns, unless otherwise specified.

Descriptive statistics will be tabulated as follows:

- Categorical data will be summarized in contingency tables presenting frequencies and percentages.
- Continuous data will be summarized using number of non-missing values (n), mean, standard deviation, median, minimum, 1st quartile (Q1), 3rd quartile (Q3), and maximum values.

Listings with individual Subjects' data will be provided for all CRF (including derived data) and central laboratory data or other external data. Data collected on the CRF that are *not* present in a table will also be listed (e.g. time and method of tonometry, comments fields, data on Fatal Outcomes page, Unscheduled Visit pages, etc.).

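### SAP 7.2, as printed, counts an eye with zero change in visual acuity as a loss

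*SAP*

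**What the plan says.** SAP 2.1.1 names visual acuity among the safety endpoints: "Ophthalmic variables (visual acuity, IOP, ophthalmologic examination, stereoscopic fundus photography". SAP 7.2 makes mean change at Month 6 the principal visual-acuity measure and adds threshold counts in support. The gain side begins at five letters: "Supportive measures will be the percentage of subjects gaining $\geq 5", then 10, 15 and 20. The loss side reads "losing $\geq 0$ , $\geq 10$ , and $\geq 15$ letters from Baseline to Month 6".

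Three other provisions bear on these rows:

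- SAP 5 defines baseline acuity as the average of the Screening score and the Day 1 pre-injection score.
- SAP 2.3 plans "10 subjects each in cohorts 1, 2 and 20 subjects each in cohorts 3, 4".
- SAP 3.3.3 sets the denominators: "subjects with missing data are generally not included in calculations of percentages unless otherwise specified".

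SAP 3.3.5 (Visual Acuity Conventions) is in the table of contents, but its text cannot be read. Part of 7.2 after the threshold sentence is also blacked out.

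**The concern.** A row labelled as loss should count subjects who lost something. With the threshold at zero, an unchanged eye enters the row. The gain side of the same sentence does not treat small or absent change this way, because its first row needs at least five letters. As printed, the lowest loss row is therefore the share without any improvement, shown under a label that says vision was lost.

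Safety is the only objective of this trial and acuity is one of its safety variables. A row that overstates the share losing vision is wrong in a place where readers will look. With 10 or 20 subjects per cohort, one misclassified eye is visible in the percentage.

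**Working it through.** The plan has no figure to reproduce here: there is no test, power calculation or expected loss rate. The check has three steps.

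**1. Which eyes meet each row.** Let change = Month 6 score − baseline score, and loss = −change.

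| Change (letters) | Loss ≥ 0 | Loss > 0 | Loss ≥ 10 | Loss ≥ 15 | Gain ≥ 5 |
|---|---|---|---|---|---|
| −15 | yes | yes | yes | yes | no |
| −10 | yes | yes | yes | no | no |
| −1 | yes | yes | no | no | no |
| 0 | **yes** | no | no | no | no |
| +1 | no | no | no | no | no |
| +5 | no | no | no | no | yes |

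The printed row and a true any-loss row differ only at change = 0.

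**2. Shift per unchanged eye.** The shift is 1/n, where n is the number with a Month 6 value.

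- Planned sizes (SAP 2.3): 1/10 = 10 points in Cohorts 1 and 2; 1/20 = 5 points in Cohorts 3 and 4.
- Missing values shrink the denominator (SAP 3.3.3). If 10% to 20% were missing (an assumption), the shift would be 1/9 = 11.1 to 1/8 = 12.5 points, or 1/18 = 5.6 to 1/16 = 6.25 points.

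**3. How many unchanged eyes to expect.** The documents give no SD, so this step is illustrative. Assume a normal change with mean m and SD s, recorded in whole letters:

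P(0) = Φ((0.5 − m)/s) − Φ((−0.5 − m)/s)

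Inputs: m from 0 (assumed) to 15.3 letters, the highest Week 24 group mean in Protocol 4.5.1; s from 10 to 15 (assumed).

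- Highest, m = 0 and s = 10: Φ(0.05) − Φ(−0.05) = 0.040.
- Middle, m = 10 and s = 12: 0.023.
- Lowest, m = 15.3 and s = 10: Φ(−1.48) − Φ(−1.58) = 0.012.

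Expected unchanged eyes are n × P(0):

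- Cohort of 10: 0.12 to 0.40.
- Cohort of 20: about 0.25 to 0.80.

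The expected excess in the row is 100 × P(0), about 1.2 to 4.0 points.

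Baseline is the mean of two scores (SAP 5). Without rounding, changes can fall on half letters. Replacing ±0.5 by ±0.25 in the formula gives P(0) of 0.006 to 0.020, about half as large.

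**The case against.** **The digit may be wrong.** The point rests on one character in text read from a PDF, and small characters in this SAP were not read reliably. In the Cohort 1 table of SAP 3.1, Day 9 carries superscript 2 and the Day 1 imaging marks carry superscript 6, while the matching footnotes are numbered 7 and 8. That does not show the zero was misread, but it is a good reason to check the source first. This stands.

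**The governing text is redacted.** A rule for zero change or for rounding would belong in SAP 3.3.5 or in the blacked-out part of 7.2. Redacted text is not missing from the plan, so the claim can only be that nothing readable settles the matter. This also stands, and confidence is low for that reason.

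**The threshold is explicit, so the rest is taste.** A reader can see that ≥ 0 includes zero, and the row is computable. This does not stand as a defence: zero change is not a loss, so the label and the count disagree whichever was intended.

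**Other outputs limit the harm.** Mean change is the principal measure, no test or decision rule uses the row, and listings of individual "data will be provided for all CRF (including derived data) and central laboratory data or other external data" allow it to be recomputed. This stands, and keeps the point minor.

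Two stronger readings are tempting, and the documents support neither.

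- A reader might set this row beside the protocol's background figures for anti-VEGF monotherapy, "approximately 20% to 30% lose additional vision from baseline" in 4.1 and "approximately 25% of the patients lose additional vision" in 4.6, and conclude that the printed rule biases that comparison. No readable text plans the comparison. The protocol does not define what counts as losing vision in those figures, and the source cited in 4.6 reports two-year results, not Month 6.
- A reader might infer from the gain side that ≥ 5 was meant, so that the printed rule would swell the row substantially. Nothing readable requires the two sides to match.

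**Conclusion.** The point holds for the text as printed: the lowest loss row equals everyone with change ≤ 0, so an unchanged eye is reported as a loss. It is minor. One supportive descriptive row is affected, by 10 points per unchanged eye in a cohort of 10 and 5 points in a cohort of 20.

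Unchanged eyes are probably few, about 1% to 4% of subjects. That range depends on a normal model, an assumed SD of 10 to 15 letters and mean changes of 0 to 15.3 letters; it roughly halves if the averaged baseline is left unrounded. Many cohorts would then contain no unchanged eye at all. Mean change and the ≥ 10 and ≥ 15 loss rows do not change.

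Confidence is low because the source digit and the redacted conventions could resolve the matter.

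**What to change.** First check the threshold, and any rule on zero change or baseline rounding, in the unredacted SAP (3.3.5 and 7.2). If ≥ 0 is what the SAP says, choose one of two corrections:

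- If the row is meant to show any loss, set it to > 0 letters.
- If a non-gainer row is meant, keep the count and label it as no gain (change ≤ 0).

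The cost is one line in the SAP and the matching table shell. No new data are needed, and no other row changes. If the source shows a different digit, or the redacted text already excludes zero, no change is needed.
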